SATISFACTION WITH AN IN-HOUSE DEVELOPED NASAL FOREIGN BODY REMOVAL MANIKIN: A RANDOMIZED-CONTROLLED TRIAL

10 Feb 2021

NCT04901026
Unique Protocol ID: 64-019-13-1

[name]
[Email address]

Background: Nasal foreign bodies can lead to life-threatening conditions. Hence, it is a necessity that physicians be well trained in the appropriate procedures for removal of nasal foreign bodies. However, training on real patients is not only unpractical it is also too dangerous, due to risk of foreign body aspiration during the procedure.

Objective: To construct a manikin, with a specific design, to serve all possible needs for training.

Design: A randomized controlled trial with a crossover design.

Methods: The in-house manikin was developed from 2 materials; flexible polyurethane foam and silicone. Silicone, which has elasticity similar to nasal alae, was used to develop the detachable nose and nasal cavity, whilst polyurethane foam, which is light and easy to carry, was used to develop the head. The in-house manikin was compared with a commercial manikin for satisfaction after a nasal foreign body removal procedure was performed in both groups, by 37 physicians, after conducting a randomized controlled trial with a crossover design.

Statistical analysis: A Wilcoxon signed-rank test was used to compare the satisfaction scores between the in-house and commercial manikin. A P value lower than 0.05 was considered as statistically significant. Simple and multiple linear regression were used to assess which variables were independently associated, with a total satisfaction score difference between the inhouse and commercial manikins. Baseline characteristics, including medical specialty, age, gender, time experience as a general physician or an ENT specialist, were assigned as independent variables. The total satisfaction score difference between the in-house and commercial manikins was assigned as a dependent variable. This total satisfaction score difference was calculated from a different value of score summations in each dimension between the in house and commercial manikins. The Shapiro-Wilk test was used to test the normality of the dependent variables. In the simple regression analysis, a threshold of a p value less than 0.1 was used to identify candidates for inclusion in the multiple linear regression.

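### Does an objective about serving every training need have to be changed when the trial measures only satisfaction?

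*Combined protocol and SAP*

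**What the plan says.** The combined protocol and SAP gives one objective: "To construct a manikin, with a specific design, to serve all possible needs for training". That sentence names no comparator, endpoint or success criterion, and the training needs are not listed.

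The rest of the document is consistent about what is compared. The title is "SATISFACTION WITH AN IN-HOUSE DEVELOPED NASAL FOREIGN BODY REMOVAL MANIKIN: A RANDOMIZED-CONTROLLED TRIAL". Methods first describes how the manikin was made (silicone for the nose and nasal cavity, polyurethane foam for the head) and then states: "The in-house manikin was compared with a commercial manikin for satisfaction after a nasal foreign body removal procedure was performed in both groups", adding that this was done "by 37 physicians, after conducting a randomized controlled trial with a crossover design".

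Statistical analysis gives the main test: "A Wilcoxon signed-rank test was used to compare the satisfaction scores between the in-house and commercial manikin". The threshold follows: "A P value lower than 0.05 was considered as statistically significant". The regressions take the difference in total satisfaction score as the dependent variable, defined thus: "This total satisfaction score difference was calculated from a different value of score summations in each dimension between the in house and commercial manikins". The dimensions are not named. The independent variables are baseline characteristics, among them specialty and length of experience as a general physician or ENT specialist.

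**The concern.** An objective normally states the question that the primary comparison answers. Here the objective speaks of meeting every training need, while the randomised comparison and all the analyses concern a satisfaction score. Physicians may like a manikin without learning more from it, and the Background rests the case for the study on competence in a hazardous procedure, not on preference. A reader who sets a significant satisfaction result beside that rationale and that objective could conclude that the in-house manikin trains physicians well, which the trial does not measure. Some raters also appear to be ENT specialists, so the scores may not be purely those of people who still need the training. If the document drew its conclusion in the terms of the objective, the conclusion would go beyond the evidence.

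**Working it through.** No figure is in dispute and no formula applies. The document gives 37 physicians and a 0.05 threshold but no effect size, standard deviation or power, so there is no stated calculation to reproduce. The check is to set the parts of the document side by side.

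| Place | What it addresses |
|---|---|
| Title | Satisfaction with the in-house manikin |
| Background | Need for physicians to be competent in removal |
| Objective | Building a manikin, with a broad training purpose |
| Methods, first part | How the manikin was built |
| Methods, second part | Satisfaction, in-house versus commercial |
| Statistical analysis, signed-rank test | Satisfaction scores |
| Statistical analysis, regressions | Difference in total satisfaction score |

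**Step 1: outcomes.** One outcome construct is described, satisfaction. The number of outcomes that measure skill, learning, retention, procedural success, time or errors is 0. The factual basis of the concern is therefore correct.

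**Step 2: what the objective asserts.** The main verb of "To construct a manikin, with a specific design, to serve all possible needs for training" is to construct. The closing phrase says what the manikin is meant for; it is not framed as a hypothesis to be tested. The first part of Methods addresses construction directly. What the sentence leaves out is the comparison, which the title and the second part of Methods supply.

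**Step 3: what each result would show.** A higher score for the in-house manikin shows preference over one commercial product. It cannot show that every training need is met. An equal or lower total score does not show that the needs are unmet. It does not follow that the scores could never count against the purpose phrase. The dimensions are unnamed, and if one of them rated suitability for training, a poor score there would weigh against so broad a claim. The firm statement is the one-sided one: satisfaction cannot establish full coverage of training needs.

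**Step 4: what rewording would alter.** Suppose the objective were restated as a comparison of satisfaction between the two manikins.

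- Data collected: the same satisfaction scores.
- Main test: the same Wilcoxon signed-rank test.
- Threshold: the same 0.05.
- Sample: the same 37 physicians.
- Regressions: the same dependent and independent variables.
- Estimates and error rates: unchanged.

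**Step 5: whether the misreading is in the document.** The text contains no conclusion, no claim of training effectiveness and no planned inference from satisfaction to skill. The risk lies in how a later reader might use the result, not in anything the plan directs an analyst to do.

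**The case for a change.** The best case for a change is that it costs almost nothing and that the objective is the one part out of step with the rest. Read literally as a construction goal, it leaves the trial's only randomised comparison without a stated objective. Read broadly, it promises something the trial cannot deliver. Either way, a sentence naming the satisfaction comparison would be better, and it would guard against over-reading in a field where the Background stresses patient danger.

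Much of this stands. The objective does omit the comparison, its purpose phrase is too broad, and a satisfaction score cannot establish that it has been met.

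Three parts do not carry over into a required change. First, the harm depends on a conclusion the document never draws, and the title and Methods tell any reader what was measured. Second, the presence of ENT specialists conflicts with nothing: the Background and Methods speak of physicians, no trainee population is defined, and specialty and experience are examined as predictors of the satisfaction difference. Third, a rewording that made the total score in a two-period crossover the compared quantity would not be neutral. The signed-rank test is applied to satisfaction scores without saying whether total or by dimension; the total is defined only for the regressions; and the number of periods is inferred, not stated. Such a rewording would settle an endpoint choice that the document leaves open.

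**Conclusion.** The concern describes a true but minor mismatch of wording. One sentence states a building goal with an overbroad purpose, while the title, Methods and Statistical analysis agree that the question is satisfaction. The effect on the analysis is nil: no data, test, threshold, sample size, estimate or error rate depends on the sentence. Measuring satisfaction instead of skill is a legitimate choice of scope, and the title declares it openly. An analyst following the document would run the satisfaction comparison and report it as such.

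This rests on two assumptions. One is that the report's conclusion stays within satisfaction, as the text gives no reason to doubt. The other is that the unnamed dimensions are parts of a satisfaction score, as the Statistical analysis section implies. If a report claimed training effectiveness from these data, the criticism would belong to that claim. The plan needs no change.

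### The signed-rank test and the regression both ignore the randomised crossover order: a common period effect would cost power near balance and cause bias if the orders are clearly unequal (minor)

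*Combined protocol and SAP*

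**What the plan says.** The Design paragraph of the combined protocol and SAP states: "A randomized controlled trial with a crossover design". The Methods paragraph says the procedure was carried out on both manikins "by 37 physicians, after conducting a randomized controlled trial with a crossover design".

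The Statistical analysis paragraph gives one between-manikin test: "A Wilcoxon signed-rank test was used to compare the satisfaction scores between the in-house and commercial manikin". A regression follows. Its outcome: "The total satisfaction score difference between the in-house and commercial manikins was assigned as a dependent variable". Its predictors: "Baseline characteristics, including medical specialty, age, gender, time experience as a general physician or an ENT specialist, were assigned as independent variables". Variables reach the multiple model through a screen: "a threshold of a p value less than 0.1 was used to identify candidates for inclusion in the multiple linear regression".

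The text mentions no order, sequence or period in either analysis. It does not give the method of randomisation or the number of physicians allocated to each order.

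**The concern.** A crossover randomises the order of use so that an effect of going first or second can be separated from the effect of the manikin. Physicians might score the second manikin higher because they have warmed up, or lower because they are tired or more critical. If that shift is the same for both manikins, it has opposite signs in the two orders once the in-house minus commercial difference is taken. An analysis that does not know the order counts the gap between orders as random variation.

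Two conclusions are exposed. The signed-rank test is the trial's only between-manikin comparison, and a moderate real difference could be missed. The regression looks for physician characteristics that explain the difference, and a real predictor could fail the p<0.1 screen or the final test. If the orders also turned out clearly unequal, part of the period effect would be credited to one manikin.

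**Working it through.** **Inputs from the document.** 37 physicians, each using both manikins; significance level 0.05 (sidedness not stated, two-sided assumed); signed-rank test; linear regression on baseline characteristics with a p<0.1 screen. The plan gives no power or sample-size figure, so there is nothing to reproduce.

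**Assumed inputs, shown as ranges.** The SD of the paired difference within an order is set to 1. The true manikin difference is d, the common period effect is π, and differences are normal. Of the 37 physicians, n1 use the in-house manikin second and n2 use it first. The closest possible split is 18/19.

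**Step 1: the model.** The in-house minus commercial difference is centred at d + π when the in-house manikin is second and at d − π when it is first.

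**Step 2: noise near balance.** Ignoring order, the SD of the differences becomes about √(1 + π²): √1.25 = 1.12 at π = 0.5 and √2 = 1.41 at π = 1.0. With the split fixed, the mean difference still has standard error 1/√37 = 0.164. An order-blind analysis of the mean would work with 1.12/√37 = 0.184 or 1.41/√37 = 0.232. The yardstick is too wide, so the analysis is conservative. The signed-rank test behaves in the same way.

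**Step 3: bias off balance.** The mean difference shifts by π(n1 − n2)/37. The multiplier of π is 1/37 = 0.027 at 18/19, 7/37 = 0.19 at 15/22 and 11/37 = 0.30 at 13/24.

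**Step 4: signed-rank test by simulation, 18/19.** Ranges cover which order has the extra physician. The order-aware test is a rank-sum test between orders on second-minus-first differences.

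| π | Type I error | Power, d = 0.485 | Power, d = 0.8 | Power, d = 1.0 |
|---|---|---|---|---|
| 0.25 | 4.3% | 77–80% | 99.5% | at least 99.6% |
| 0.5 | 2.8% | 69–75% | 99% | at least 99.6% |
| 1.0 | 0.5% | 40–54% | 94–97% | at least 99.6% |
| Order-aware, any π | about 5% | 79–80% | 99.6% | about 100% |

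**Step 5: signed-rank test, unequal orders.**
- 15/22: type I error is at most about 5.6%. At d = 0.485 and π = 0.5, power is 51% or 87% depending on which order is larger, against 78% order-aware.
- 13/24: type I error is 6.4% (π = 0.25), about 10% (0.5) and 17% (1.0). At π = 1.0, power for d = 0.485 is 4% or 97%, against 76% order-aware. For d = 1.0 it falls to 85% in the adverse direction.
- Under simple randomisation, a 13/24 or worse split has probability 9.9% (binomial, 37 trials, probability 0.5).

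**Step 6: regression by simulation, 18/19.** The model has one binary baseline variable with slope 0.48 (SDs of the difference per covariate SD).

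| π | Power without order | Power with order | Passes p<0.1 screen without order | Passes with order |
|---|---|---|---|---|
| 0 | 81% | 80% | – | – |
| 0.25 | 79% | 80% | 87% | 88% |
| 0.5 | 72% | 80% | 82% | 88% |
| 1.0 | 51% | 80% | 64% | 88% |

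These figures do not depend on d, because d only moves the intercept; runs at d = 0 and d = 3 agree. The slope is unbiased and its type I error is 5% with or without the order term.

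**The case against.** The paired test is a valid choice for a crossover when there is no period effect, and nothing in the document shows that there is one. Near balance the error is on the cautious side, and averaged over simple randomisation the type I error is 5%. The losses are small in much of the range: at 18/19 with π = 0.25 and d = 0.485, about 0–3 points; with π = 0.5 and d = 0.8, under 1 point. The drop of about 40 points needs a period effect of a full SD, a moderate true difference and the unfavourable placing of the odd physician. The simulations also assume continuous normal differences, while the real scores are sums over dimensions on an unstated scale, where ties and ceiling effects are possible. All of this stands, and it is why the point is minor.

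The word introducing the covariate list leaves it open to additions. That does not rescue the regression: order is not a baseline characteristic and is named nowhere.

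A reader might infer that a large manikin difference makes the whole issue disappear. That holds only for the signed-rank test with near-equal orders. It does not hold for the regression at any d, nor for the signed-rank test at 13/24, where power at d = 1.0 can fall to 85%. A reader might also infer that the trial's comparison is wrong or carries an inflated false-positive rate. The document does not support that, because it gives neither the split nor any sign of a period effect.

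**Conclusion.** The omission is certain: neither analysis, as described, uses the randomised order. Its size is not known. With near-equal orders and a common period effect of 0.5 to 1.0 SD, the signed-rank test is conservative and loses roughly 4 to 40 points of power at d = 0.485, and almost nothing at d of about 1 or more. The regression loses about 8 to 29 points at slope 0.48, whatever the manikin difference. With clearly unequal orders the problem for the manikin comparison is bias, and power can be far too low or too high depending on direction.

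All these sizes rest on assumed values for the period effect, the true difference, the slope and the split, and on normal differences. None comes from the document. Severity is minor.

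**What to change.** - Add order, coded +1/−1, as a fixed term in the simple and multiple regressions, exempt from the p<0.1 screen. At 18/19 the screen would drop a period effect of 0.25 SD 56% of the time and one of 0.5 SD 9% of the time.
- Beside the signed-rank test, report a rank-sum test between the two orders on each physician's second-minus-first difference. Give half the Hodges-Lehmann shift, with its 95% CI, as the in-house minus commercial difference.
- The document is written in the past tense. If the data have been analysed, keep the signed-rank test as the main test and label the order-aware result post hoc.
- Report the randomisation method and the number of physicians in each order.

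**Cost.** Wording and a few lines of code, provided the allocated order was recorded, which the document does not say. With no period effect, at d = 0.485, the order-aware test loses under 1 point of power at 18/19 (80.1% to 79.6%), about 2 points at 15/22 (79.9% to 77.8%) and about 4 points at 13/24 (79.9% to 75.9%). The regression loses about 1 point (81.2% to 80.0%).

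**Limit.** The change does not address carryover or an order effect specific to one manikin. If only the commercial manikin, when used second, shifted by 0.5 SD, with 18/19 and no true difference, type I error would be 27–29% for the signed-rank test and 30% for the order-aware test. The report should say so.

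### Does leaving the deciding satisfaction score unnamed push the false-positive rate above 5%?

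*Combined protocol and SAP*

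**What the plan says.** The comparison between manikins is set out in two sentences of the Statistical analysis section. The first names the test: "A Wilcoxon signed-rank test was used to compare the satisfaction scores between the in-house and commercial manikin". The second gives the threshold: "A P value lower than 0.05 was considered as statistically significant". Neither says which score is meant, and sidedness is not stated.

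A total appears further on, in the description of the regression: "The total satisfaction score difference between the in-house and commercial manikins was assigned as a dependent variable". Its construction is described this way: "This total satisfaction score difference was calculated from a different value of score summations in each dimension between the in house and commercial manikins". So the questionnaire has more than one dimension and there is a total across dimensions. The number of dimensions is not given.

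The Objective, "To construct a manikin, with a specific design, to serve all possible needs for training", mentions no score. The Methods section gives the size and pairing: manikins were compared "after a nasal foreign body removal procedure was performed in both groups, by 37 physicians", in a crossover. No primary outcome, testing order or multiplicity adjustment is named.

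**The concern.** Satisfaction is the only comparison between the two manikins in the plan, and it is in the trial's title. A reader who finds several dimension scores, a total, one unadjusted threshold and no named primary score will reasonably ask which result counts. If any significant dimension could be put forward as showing that satisfaction differs, the 5% level would not apply to that overall conclusion. If dimensions pointed in opposite directions, the plan would not say which one answers the question. At stake is whether a reported difference in satisfaction carries the error rate that the 0.05 threshold suggests.

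**Working it through.** **Inputs**

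- Threshold per test: 0.05 (Statistical analysis). Two-sided is assumed.
- Pairs: 37 physicians, each using both manikins (Methods).
- Number of scores tested, k: not stated; 2, 3 and 5 assumed.
- Correlation between scores, rho: not stated; 0 to 0.9 assumed. Ratings by the same physician are probably positively correlated, so rho = 0 is taken as the upper end.

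The plan gives no overall error rate or sample-size derivation, so there is no figure of its own to reproduce.

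**1. One score decides.** The rate is 1 − 0.95 = 0.05. Signed-rank tests of the total alone on 37 simulated pairs gave 4.7% to 5.2%. There is no inflation.

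**2. Any of k scores decides, either direction.** For independent tests the rate is 1 − 0.95^k:

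- k = 2: 1 − 0.9025 = 9.75%
- k = 3: 1 − 0.8574 = 14.3%
- k = 5: 1 − 0.7738 = 22.6%

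With equally correlated normal test statistics (400,000 draws):

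| k | rho 0.5 | rho 0.7 | rho 0.9 |
|---|---|---|---|
| 2 | 9.1% | 8.4% | 7.0% |
| 3 | 12.5% | 11.0% | 8.3% |
| 5 | 18.2% | 14.9% | 10.2% |

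A simulation of 40,000 trials with signed-rank tests on 37 pairs agrees: 7.3% (k = 2, rho 0.9), 12.6% (k = 3, rho 0.5) and 18.5% (k = 5, rho 0.5). Testing the total as well adds at most about 2 percentage points.

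**3. Any of k scores decides, but only results favouring one named manikin count.** Each two-sided test then contributes 0.025. For independent tests the rate is 1 − 0.975^k:

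- k = 2: 1 − 0.9506 = 4.9%
- k = 3: 1 − 0.9269 = 7.3%
- k = 5: 1 − 0.8811 = 11.9%

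At rho 0.9 these fall to 3.5%, 4.2% and 5.1%. All exceed the 2.5% that applies to one direction. With two tests, however, the rate cannot pass 2 × 0.025 = 5%. A general statement that the rate exceeds 5% therefore needs results in either direction to count.

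**4. Which of these rules does the text contain?** The test sentence speaks of one test. The plural in it proves little: paired data give one score per physician per manikin, so even a single outcome produces scores. The evidence for several dimensions is the phrase "calculated from a different value of score summations in each dimension between the in house and commercial manikins", which explains how the regression outcome is built. Nowhere does the text say that dimensions are tested separately, or that one significant dimension is enough. Steps 2 and 3 therefore describe a rule that the plan leaves open but does not state. Step 1 describes the result if the only overall score it names decides. If each dimension is reported as a claim about that dimension alone, each test also keeps its own 5% level.

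**The case for a change.** The strongest case for a change is that the total is given only to the regression, and a choice the reader has to infer is not pre-specified. Opposing dimensions add a difficulty that needs no assumption about k or rho: nothing says which result prevails. The remedy would also be cheap, one sentence naming the total as the primary comparison and the dimensions as secondary.

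Much of this stands. The omission is real, and the paragraph is complete enough that missing text does not explain it. The arithmetic is also right under its condition.

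What does not stand is the step from an unnamed score to a faulty error rate. That step needs a decision rule that is not in the document, together with a number of dimensions and a correlation that are not there either. Naming the total would mostly write down the choice an analyst would already make, and it would not settle opposing dimensions, since a total can conceal them; they would still have to be shown side by side. The section is also written in the past tense. If scores had already been seen, naming a primary score now could not restore error control, and only disclosure would remain.

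**Conclusion.** The plan does not say which satisfaction score the Wilcoxon test uses or which one decides the comparison. This is missing detail that analysts can fill sensibly with the total, and the 5% level then holds (4.7% to 5.2% in simulation). An inflated rate, illustratively 7% to 23% for two to five tests, arises only if dimensions are tested separately at an unadjusted two-sided 0.05 and any significant result in either direction is turned into an overall claim. That range rests on assumed k and rho and does not measure this trial. For claims favouring one named manikin with two tests, the rate stays at or below 5%. The conclusion depends on the total being read as the overall score. A report that instead built an overall claim on one selected dimension should be read with the figures above in mind. No change to the plan follows.

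### The unadjusted p<0.1 entry rule can drop a masked variable before adjustment, although the regression is meant to find independent associations (low severity, secondary analysis only)

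*Combined protocol and SAP*

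**What the plan says.** All the relevant text is in the Methods and Statistical analysis paragraphs of the combined protocol and SAP.

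- **Aim:** "Simple and multiple linear regression were used to assess which variables were independently associated" with the difference in total satisfaction score.
- **Outcome:** "The total satisfaction score difference between the in-house and commercial manikins was assigned as a dependent variable".
- **Candidates:** "Baseline characteristics, including medical specialty, age, gender, time experience as a general physician or an ENT specialist, were assigned as independent variables". Experience may be one term or two, and the list is introduced as non-exhaustive.
- **Entry rule:** in the simple regressions, "a threshold of a p value less than 0.1 was used to identify candidates for inclusion in the multiple linear regression".
- **Sample:** "a nasal foreign body removal procedure was performed in both groups, by 37 physicians".
- **Significance:** "A P value lower than 0.05 was considered as statistically significant". Sidedness is not stated, and two-sided is assumed below.

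No variable is said to be forced into the multiple model. No re-entry step or subject-matter rule for choosing covariates is described.

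**The concern.** An independent association is one that remains after adjustment. The entry rule looks only at the unadjusted association. The two differ when covariates are correlated and both affect the outcome. If their effects oppose each other in the hiding direction, the crude slope shrinks towards zero, the variable fails p<0.1, and the adjusted model that would have shown it is never fitted with that variable in it.

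The listed covariates are unlikely to be uncorrelated. Age stands beside length of experience, and experience is described by role beside specialty. At stake is a missed characteristic in the analysis of who prefers which manikin. A variable that was screened out would have a crude result but no adjusted estimate.

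**Working it through.** The plan gives no power or error-rate figure for the regression, so there is nothing to reproduce. The check asks whether the mechanism matters at this sample size.

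**From the documents:** n = 37; entry at crude p<0.1; significance at 0.05; four listed variables (specialty, age, gender, experience).

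**Assumed, because the documents give none:** residual SD 1; specialty binary with 40% in one group; gender 50:50; age standardised and correlated r with specialty; experience correlated 0.85 with age; all variables passing the screen entered together; two-sided tests.

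**Step 1. Crude against adjusted effect.** The SD of specialty is √(0.4 × 0.6) = 0.490. The crude specialty effect is

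crude = β(specialty) + β(age) × r / 0.490.

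With β(specialty) = 1.0, β(age) = -0.5 and r = 0.5, crude = 1.0 - 0.5 × 0.5 / 0.490 = 0.49. The adjusted effect is 1.0, so about half of it is hidden.

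**Step 2. Chance of passing the screen, by hand.** The SD around the crude regression is √(1 + 0.25 × 0.75) = 1.09. The crude SE is about 1.09 / (0.490 × √37) = 0.366, so the expected t is 0.49 / 0.366 = 1.34. The p<0.1 cut-off on 35 df is 1.69. The chance of passing is about P(Z > 1.69 - 1.34) = P(Z > 0.35) = 36%. Simulation gives 36% as well.

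**Step 3. Power for specialty (p<0.05 in the final model), by simulation.**

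| Setting | Crude effect | Under the rule | All four fitted |
|---|---|---|---|
| +1.0, age -0.5, r 0.2 | 0.80 | 61% | 75.5% |
| +1.0, age -0.5, r 0.35 | 0.64 | 45% | 72% |
| +1.0, age -0.5, r 0.5 | 0.49 | 28-29% | 65-66% |
| +1.0, age -0.5, r 0.7 | 0.29 | 12% | 50% |
| +1.0, age -0.25, r 0.5 | 0.74 | 54% | 66% |
| +0.5, age -0.25, r 0.5 | 0.24 | about 10% | about 22% |
| +1.0, age +0.5, r 0.5 | 1.51 | 66% | 65% |
| +1.0, age 0, r 0.5 | 1.00 | 68-69% | 64-65.5% |
| +1.0, age -0.5, r -0.5 | 1.51 | 67% | 66% |

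The loss does not depend on age being the hiding variable. With experience at -0.5 in place of age, power is 36% against 65%. With age and experience at -0.25 each, it is 32% against 65%.

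**Step 4. A simpler design as a cross-check.** With two normal covariates, slopes 0.6 and -0.6 and n = 37, power under the rule against both fitted is 65% vs 89%, 39% vs 82%, 16% vs 68% and 9% vs 54% at correlations 0.3, 0.5, 0.7 and 0.8. If the second slope is zero and the correlation 0.5, it is 85% vs 83%, so there is no loss.

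**Step 5. False positives.** With all four effects null, the chance of at least one p<0.05 is about 11-12% under the rule and 16% with all four fitted.

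**Step 6. Room for the full model.** Residual df = 37 - 1 - 4 = 32 with four single-df terms, and 31 with five.

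**The case against.** The strongest reply is that the harm is conditional. It needs correlated covariates whose effects oppose each other in the hiding direction, and the documents give no reason to expect that sign. When the effects have the same sign, when age has no effect, or when the specialty/age correlation is reversed, the rule loses nothing and can do slightly better. The headline figures also use a large specialty effect. With both effects halved, the full model reaches only about 22%, so removing the screen does not rescue a modest effect in 37 physicians. All of this stands. It limits the weight of the point, but the rule still works against its stated aim.

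Three stronger readings are tempting and are not supported.

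- **That screening and fitting in the same 37 physicians inflates false positives.** Among null variables that pass the screen, a large share go on to p<0.05 (44-49% with four or five uncorrelated candidates). That figure is conditional on having passed p<0.1. Over all runs the rule gives fewer any-false-positive results than the full model. Exaggerated estimates among selected variables also come from reading only results past a threshold. A true gender effect of 0.5 averages 0.78 when kept by the rule, and 0.81 in an unscreened model of specialty, age and gender if only p<0.1 results are read. The effect is not specific to the screen.
- **That only screened-in variables will be reported.** The plan contains no reporting rule, and the simple regressions give a crude result for every listed variable.
- **That an association has been missed in this trial.** Nothing in the documents shows this.

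**Conclusion.** The point holds in a limited form. The entry rule does not match the aim of finding independent associations, and at n = 37 it can remove a masked variable that the full model would have a fair chance of detecting. In the central assumed case the loss is about 37 percentage points of power (28-29% against 65-66%). It ranges from about 15 points at specialty/age r 0.2 to none where the effects do not oppose. These sizes rest wholly on assumed effects, correlations and group proportions. The mechanism does not depend on those values, but its occurrence in this trial is unknown.

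Severity is low. This is an optional improvement to a secondary regression. A reader might infer that the manikin comparison is affected. It is not: the Wilcoxon signed-rank test does not use the regression.

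**What to change.** Delete the p<0.1 screen. As the main model, fit one multiple linear regression with all listed baseline variables: specialty, age, gender and experience. Report every coefficient with its 95% CI whatever its p-value. Label the analysis exploratory and keep the simple regressions as descriptive.

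A model without age or without experience should be shown only as a sensitivity analysis, because leaving out the one that matters can bias specialty. In the central case, with experience standing in for age, the specialty estimate averages 0.82 for a true 1.0, and 0.59 if age and experience correlate only 0.5. With no specialty effect, age -0.5 and age/experience correlation 0.5, specialty is falsely significant in about 17-18% of runs, against 3% under the rule and 5% with all four fitted.

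The cost is a wording change and one model fit. Four single-df terms leave 32 residual df, and fewer if specialty or experience needs more terms. Intervals for age and experience widen because the two are likely to be collinear. In the assumed set-up, adding experience to specialty, age and gender raises the SE for age from 0.20 to 0.35 and, in the central case, lowers its power from 67% to 29%. Power for specialty barely moves (67% to 65%).

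The text is in the past tense. If the analysis has already been run, refit without the screen, report all coefficients and state that the change was made afterwards.
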